10.7 Assessment of expectedness of an SAE by the CI

The CI or delegate will assess related SAEs for expectedness with reference to the criteria in **Table 8**.

Table 8: Categories of expectedness

Category	Definition
Expected	An adverse event that is consistent with known information about the trial related procedures, trial intervention (as described in the manufacturer's guidance) or pre-existing conditions of the participant (including DM).
Unexpected	An adverse event that is not consistent with known information about the trial related procedures, trial intervention, or pre-existing conditions of the participant.

If the event is unexpected (i.e. it is not defined in the protocol as an expected event) it will be classified as a related and unexpected SAE.

The CI will undertake review of all SAEs and may request further information from the clinical team at site for any given event to assist in this.

10.8 Provision of SAE follow-up information

Following reporting of an SAE for a participant, the participant should be followed up until resolution or stabilisation of the event. Follow-up information should be provided using the SAE reference number provided by the Trial Office. Once the SAE has been resolved, all critical follow-up information has been received and the paperwork is complete, a copy of the final version of the completed SAE form must be submitted to the Trial Office and a copy printed to be stored in the ISF.

10.9 Reporting SAEs to third parties

The independent Data Monitoring Committee (DMC) may review any SAEs at their meetings.

The Trial Office will submit a progress report to the Research Ethics Committee (REC) and University of Birmingham (UoB) Research Governance Team (RGT) annually starting 12 months after the date of the favourable opinion was given. An electronic copy should be emailed to the REC within 30 days of the end of the reporting period.

The Trial Office will report all events categorised as Unexpected and Related SAEs to the REC and RGT within 15 days of being notified.

Details of all Unexpected and Related SAEs and any other safety issue which arises during the course of the trial will be reported to the PIs. A copy of any such correspondence should be filed in the ISF and Trial Master File (TMF).

11. DATA HANDLING AND RECORD KEEPING

11.1 Source data

Source data is defined as all information in original records and certified copies of original records of clinical findings, observations, or other activities in a clinical trial necessary for the reconstruction and evaluation of the trial. In order to allow for the accurate reconstruction of the trial and clinical management of participants, source data will be accessible and maintained.

In FREMS-PDPN, some data variables may be entered directly onto the CRF; these are clearly identified and detailed in **Table 9:** Source data in FREMS-PDPN.

Table 9: Source data in FREMS-PDPN

Data	Source
Participant Reported Outcomes	The original completed eCRF on the BCTU database is the source and will be held on BCTU servers. If the participant completes paper forms, the original paper copies are the source data and sites will upload this data to the trial database.
Pain Numerical Rating Scale	The participant's responses as received directly by the eCRF by text or email are the source data, and will be held on BCTU servers.
Baseline, end of treatment and 3/6 month CRFs	Data is entered directly onto the eCRF which is the source. It is held on BCTU servers.
Clinical event data	The original clinical annotation is the source document. This may be found on clinical correspondence, or electronic or paper participant records. Clinical events reported by the participant, either in or out of clinic (e.g. phone calls), must be documented in the source documents.
Recruitment	The randomisation eCRF is the source. It is held on BCTU servers.
Change of status	The change of status form is the source data and will be held on BCTU servers. This form will be completed by site research staff directly onto the eCRF.

11.2 Case Report Form (CRF) completion

The CRFs will include (but will NOT be limited to) the following Forms (see **Table 10**).

Table 10: Case report forms in FREMS-PDPN

Form Name	Schedule for submission
Consent Form	At the point of completing eligibility screening
Pain diary	Automatic submission upon completion – should be completed daily
Informed Consent Form	At the point of consent
Participant Contact Details Form	At the point of consent
Baseline CRF	As soon as possible after consent
Randomisation CRF	At the point of randomisation
End of treatment CRF	As close to the end of treatment date as possible
3-month CRF	As close to the 3 month follow up time point as possible
6-month CRF	As close to the 6 month follow up time point as possible
Change of Status Form	At the point of change of status, withdrawal or death
SAE reporting Form	At the point of being aware of an SAE

A CRF should be completed for each individual participant. Data should be submitted in a timely manner i.e. within four weeks of submission schedule.

In all cases it remains the responsibility of the PI to ensure that the CRF has been completed correctly and that the data are accurate. This will be evidenced by the electronic sign off of the PI or delegate. The Site Delegation Log will identify all those personnel with responsibilities for data collection.

The delegated staff completing the CRF should ensure the accuracy, completeness and timeliness of the data reported. This will be evidenced by the electronic sign off of the CRF.

Data reported on each CRF will be consistent with the source data and any discrepancies will be explained. All missing and ambiguous data will be queried. Staff delegated to complete CRFs will be trained to adhere to FREMS-PDPN CRF completion guidelines.

The following guidance applies to data and partial data:

- Time format – all times should be in accordance with the 24hr clock.
- Rounding conventions – rounding should be to the nearest whole number: If the number you are rounding is followed by 5, 6, 7, 8, or 9, round the number up. **Example:** 3.8 rounded to the nearest whole number is 4. If the number you are rounding is followed by 1, 2, 3 or 4, round the number down. **Example:** 3.4 rounded to the nearest whole number is 3.
- Trial-specific interpretation of data fields – where guidance is needed additional information will be supplied.
- Entry requirements for concomitant medications (generic or brand names) – generic names should be used where possible.
- Missing/incomplete data – should be clearly indicated – all blank fields will be queried by the Trial Office.
- Protocol and GCP non-compliances should be reported to the Trial Office on discovery.

11.3 Participant completed questionnaires

The NRS pain diary will be completed daily, with text reminders (or optional emails) sent to complete by return text.

Other participant completed questionnaires can be completed on paper in clinic (to be entered by site staff) or online as per participant preference. If completed in clinic, the participant will complete under the supervision of a local researcher, who should ensure completeness. If completed remotely, a reminder and link will be sent to the participant at the due date by text or email as per participant preference. If not completed within 7 days, an additional reminder will be sent.

Questions relating to suicidal thoughts are asked in some of the participant completed questionnaires. Should the patient answer yes to these there will be a pre-programmed trigger built into the ReDCAP system alerting sites that the patient has flagged as a risk. It will be the sites responsibility to act accordingly and follow this up with the patient in line with their local policy.

11.4 Data management

Processes will be employed to facilitate the accuracy and completeness of the data included in the final report. These processes will be detailed in the trial specific Data Management Plan and include the processes of data entry and data queries.

Data entry will be completed by the sites via a bespoke BCTU ReDCAP trial database. The data capture system will conduct automatic range checks for specific data values to ensure high levels of data quality. Queries will be raised using data clarification forms (DCFs) via the trial database, with the expectation that these queries will be completed by the site within 30 days of receipt. Overdue data entry and data queries will be requested on a monthly basis.

11.5 Self-evident corrections

No self-evident corrections will be permitted in FREMS-PDPN.

11.6 Data security

UoB has policies in place which are designed to protect the security, accuracy, integrity and confidentiality of Personal Data. The trial will be registered with the Data Protection Officer at UoB and will hold data in accordance with the Data Protection Act (2018 and subsequent amendments). The Trial Office has arrangements in place for the secure storage and processing of the trial data which comply with UoB policies.

The Trial Database System incorporates the following security countermeasures:

Physical security measures: restricted access to the building, supervised onsite repairs and storages of back-up tapes/disks are stored in a fire-proof safe.

Logical measures for access control and privilege management: including restricted accessibility, access-controlled servers, separate controls of non-identifiable data.

Network security measures: including site firewalls, antivirus software and separate secure network protected hosting.

System management: the system will be developed by the Programming Team at the Trial Office and will be implemented and maintained by the Programming Team.

System design: the system will comprise of a database and a data entry application with firewalls, restricted access, encryption and role-based security controls.

Operational processes: the data will be processed and stored within BCTU.

System audit: The system will benefit from the following internal/external audit arrangements:

- Internal audit of the system
- Periodic IT risk assessment

Data Protection Registration: UoB's Data Protection Registration number is Z6195856.

11.7 Archiving

It is the responsibility of the PI to ensure all essential trial documentation and source documents (e.g. signed ICFs, Investigator Site Files, participants' hospital notes, copies of paper CRFs) at their site are securely retained for the contractual period (at least 10 years). Archiving will be authorised by BCTU on behalf of UoB following submission of the end of trial report. No documents should be destroyed without prior approval from the BCTU Director or their delegate.

The TMF will be stored at BCTU for at least 3 years after the end of the trial. Long-term offsite data archiving facilities will be considered for storage after this time; data will be stored securely and confidentially for at least 10 years. BCTU has standard processes for both hard copy and computer database legacy archiving.

12. QUALITY CONTROL AND QUALITY ASSURANCE

12.1 Site set-up and initiation

All PIs will be asked to sign the necessary agreements including a Site Delegation log between the PI and the Trial Office, a site agreement between site and Sponsor, and supply a current CV and GCP certificate. All members of the site research team are required to sign the Site Delegation Log, which details which tasks have been delegated to them by the PI. The Site Delegation Log should be kept up to date by the PI. It is the PI's responsibility to inform the Trial Office of any changes in the site research team.

Prior to commencing recruitment, each recruiting site will undergo a process of site initiation, either a meeting or a videoconference, which key members of the site research team are required to attend, covering aspects of the trial design, protocol procedures, AE reporting, collection and reporting of data and record keeping. Sites will be provided with an ISF containing essential documentation, instructions, and other documentation required for the conduct of the trial.

12.2 Monitoring

The central and on-site monitoring requirements for this trial have been developed in conjunction with the trial specific risk assessment and are documented in the trial specific monitoring plan.

12.3 On-site monitoring

For this trial, all sites will be monitored in accordance with the trial risk assessment and monitoring plan. Any monitoring activities will be reported to the Trial Office and any issues noted will be followed up to resolution. Additional on-site monitoring visits may be triggered. PIs and site research teams will allow the FREMS-PDPN trial staff access to source documents as requested. The monitoring will be conducted by BCTU/UoB staff.

12.4 Central monitoring

The Trial Office will check received ICFs and CRFs for compliance with the protocol, data consistency, missing data and timing at a frequency and intensity determined by the Data Management Plan. Sites will be sent DCFs requesting missing data or clarification of inconsistencies or discrepancies.

12.5 Audit and inspection

The Investigator will permit trial-related monitoring, audits, ethical review, and regulatory inspections at their site and provide direct access to source data/documents. This will be done both on site and remotely. The investigator will comply with these visits and any required follow-up. Sites are also requested to notify the Trial Office of any relevant inspections or local audits.

12.6 Notification of Serious Breaches

The sponsor is responsible for notifying the REC of any serious breach of the conditions and principles of GCP in connection with that trial or of the protocol relating to that trial. Sites are therefore requested to notify the Trial Office of any suspected trial-related serious breach of GCP and/or the trial protocol as soon as they become aware of them. Where the Trial Office is investigating whether or not a serious breach has occurred, sites are also requested to co-operate with the Trial Office in providing sufficient information to report the breach to the REC where required and in undertaking any corrective and/or preventive action.

Sites may be suspended from further recruitment in the event of serious and persistent non-compliance with the protocol and/or GCP, and/or poor recruitment.

13. END OF TRIAL DEFINITION

The end of trial will be the date of the last data capture including confirmation of resolution of all DCFs. This will allow sufficient time for the completion of protocol procedures, data collection and input and data cleaning. The Trial Office will notify the REC and the Sponsor within 90 days of the end of trial. Where the trial has terminated early, the Trial Office will notify the REC and the sponsor within 15 days of the end of trial. The Trial Office will provide the REC and the Sponsor with a summary of the clinical trial report within 12 months of the end of trial.

14. STATISTICAL CONSIDERATIONS

14.1 Sample size

The justification for the sample size is based on the placebo response from RCTs in PDPN which is estimated to be 1.4 (95% CI 1.2 to 1.6) points reduction in pain severity based on NRS [79]. The minimum clinically relevant improvement in pain severity in pain trials is determined as 2 points on the NRS (equivalent to 30% reduction in pain) [45, 80].

To detect a mean difference of 0.6 points between groups at 3 months using the standard method of difference between means using 2-sided t-test and assuming a standard deviation of 1.65 [81] (effect size 0.36) with 90% power and a type I error rate of 5%, a total of 160 participants per group will need to be randomised, 320 in total. Assuming and adjusting for a 10% attrition rate, 356 participants will need to be recruited (178 per group) [82].

14.2 Analysis of outcomes

A separate Statistical Analysis Plan will be produced and will provide a more comprehensive description of the planned statistical analyses. A brief outline of the planned analyses is given below.

The primary comparison groups will be composed of those randomised to FREMS and standard care versus those randomised to TENS and standard care. In the first instance, all analyses will be based on the intention to treat principle, i.e. all participants will be analysed in the intervention group to which they were randomised irrespective of adherence to randomised intervention or protocol deviations.

For all outcomes, appropriate summary statistics and differences between groups, e.g. mean differences will be presented, with 95% confidence intervals and p-values from two-sided tests also provided. Where possible intervention effects will be adjusted for the minimisation variables listed in Section **Error! Reference source not found**. Randomisation and Blinding as well as baseline values. No adjustment for multiple comparisons will be made.

14.3 Primary outcome

The primary outcome measure is the 7-day average 24-hour pain score on an 11-point NRS scale (0 = no pain and 10 = worst pain imaginable) measured at 3 months post-randomisation. This is a continuous measure so linear regression methods will be used if the outcome is sufficiently normally distributed (or where data can be suitably transformed), to calculate an adjusted mean difference and 95% confidence interval. The p-value relating to the intervention group parameter as generated by the model will be presented.

14.4 Secondary outcomes

Continuous outcomes will be analysed in a similar way to the primary outcome.

Binary data will be presented as number and percentage. A log-binomial regression model will be used to calculate the adjusted relative risk and 95% confidence interval. The adjusted absolute difference and 95% confidence interval between groups will also be reported. The p-values relating to the intervention group parameter as generated by the model will be presented.

14.5 Planned subgroup analyses

Subgroup analyses will be limited to the same variables used in the minimisation algorithm (see Section 5) and performed on the primary outcome and NPSI only. The effects of these subgroups will be examined by including an intervention group by subgroup interaction parameter in the regression model, which will be presented alongside the effect estimate and 95% confidence interval within subgroups. The results of subgroup analyses will be treated with caution and will be used for the purposes of hypothesis generation only.

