1.5.5 Uncontrolled data from the Netherlands

These data are from Elisabeth-Tweesteden Hospital, Tilburg and Bethesda Diabetes Research Centre, Hoozeveen. This was an uncontrolled prospective study of patients with PDPN and persistent pain despite at least two lines of pharmacotherapy (including pregabalin or duloxetine or similar as per NICE guideline). The primary outcome was 50% reduction in pain scores at 1 and/or 3 months post-FREMS. In responders, FREMS was repeated every 4 months up to 12 months. FREMS was applied to both legs below the knees using 4 sets of electrodes per leg; the treatment consisted of 10 sessions of 35 minutes given over 14 days. Pain was assessed using the Neuropathic Pain Symptom Inventory (NPSI) and QoL was assessed using the EQ-5D-5L.

248 patients met the inclusion criteria; 56% male, average age 65 years old, and average diabetes duration 12.6 years. Before FREMS treatment, the average NPSI was 50±18. This improved after 1 and 3 months to 34±20 and 32±20 respectively ($p<0.001$ vs baseline). This improvement was maintained at 12 months ($p<0.001$). 50% decreases in NPSI scores (which is considered the ideal response) were seen in 80/248 (32.2%) at month 1 and in 87/248 (35.1%) at month 3. One third reduction in pain scores (which is considered clinically meaningful) occurred in 111 (44.8%) patients at month 1, and 123 (49.6%) at month 3.

The EQ-5D-5L VAS improved from 52.6±15.9 to 62.8±14.6 and 63.6±16.7% at months 1 and 3 respectively ($P<0.001$ vs baseline).

All of these improvements in pain scores, QoL and disability scores occurred in the context of a reduction of neuropathic pain medications over a 12 month period, including stopping opioids (unpublished data under peer review).

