2.2.4 Subgroup study objectives (exploratory objectives)

To conduct a subgroup analysis to investigate if patient phenotypes (demography, diabetes type, type of pain, mood, sleep and quantitative sensory testing profiles) predict response to treatment.

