6.4.2 Randomisation method

Participants will be randomised at the level of the individual in a 1:1 ratio to either FREMS or TENS via a secure web-based system at BCTU. The randomisation will use a minimisation algorithm to ensure balance in the treatment allocation taking into account centre, age (18-39, 40-59, 60+), gender at birth, diabetes type, ethnicity (White, Asian/Asian British, Black/African/Caribbean/Black British, Other ethnic group) and opioid use (yes/no). To avoid the possibility of the intervention allocation becoming predictable, a random element will be included in the algorithm. Full details of the randomisation specification will be stored in a confidential document at BCTU.

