8. OUTCOME MEASURES

8.1 Internal pilot outcomes

1. To assess the feasibility of identifying eligible patients.
2. To assess the acceptability of randomisation to receive the intervention or not.
3. To determine if the pilot phase should continue to a full trial.

The stop/go criteria will be assessed after 6 months of recruitment. The internal pilot's primary criteria will assess recruitment per centre per month. The target recruitment for each site will be 2 participants per month. With staggered opening of sites (2 sites per month), it is anticipated that at 6 months, 22% of the total recruitment target will have been met. Therefore, the internal pilot recruitment target is 80 participants.

We will apply a traffic light system as described below:

- Green: ≥100% of mean target recruitment per centre per month: progress to full trial.
- Amber: 60%-99% of target recruitment per centre per month: discuss feasibility with the Trial Steering Committee (TSC) and develop improvement plans. Aspects evaluated to guide improving recruitment will include: number of eligible patients identified, percentage of patients randomised and reasons for non-randomisation, recruitment site performance, and review of recruitment procedures.
- Red: <60% of the target recruitment per centre per month: Discuss cessation of the trial with the TSC and the trial funder, the National Institute for Health Research (NIHR).

Note: In light of the ongoing uncertainties during the COVID-19 pandemic and ongoing disruption to health and Research and Development Services, additional actions (e.g. increasing number of sites opened) to support recruitment may be necessary to achieve the pilot targets in an appropriate timeframe.

Table 4: Internal pilot progression criteria

Internal pilot recruitment target = 80 participants by 6 months			
	Red	Amber	Green
Participants recruited per centre per month	<1.2	1.2-1.9	≥2
% of target recruitment per centre per month	<60%	60%-99%	≥100%
Number of centres opened (NB: out of 10)	<6	6-7	≥8

We will also consider the following throughout the internal pilot to determine if changes to trial processes are required: adherence (as a percentage of treatment sessions completed), and proportion of potentially eligible patients screened.

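### Section 14.5 ties subgroup analyses to the minimisation variables, so age is tested in three allocation bands and centre becomes a subgroup of about ten levels; age in years, and no single-centre effects, would serve the exploratory aim better

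*Protocol*

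**What the plan says.** Protocol section 14.5 sets the rule: "Subgroup analyses will be limited to the same variables used in the minimisation algorithm". It applies to the primary outcome and the NPSI. The method is "including an intervention group by subgroup interaction parameter in the regression model", shown with the effect and 95% confidence interval inside each subgroup. The results "will be treated with caution and will be used for the purposes of hypothesis generation only".

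The variables are defined in section 6.4.2, where the algorithm works by "taking into account centre, age (18-39, 40-59, 60+), gender at birth, diabetes type, ethnicity" (four groups) and opioid use. Centre is on that list and section 14.5 does not exempt it. Age appears there only in bands.

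The aim that these analyses serve is in section 2.2.4: to see whether "patient phenotypes (demography, diabetes type, type of pain, mood, sleep and quantitative sensory testing profiles) predict response to treatment". Demography comes first in that list. Centre is not in it.

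**The concern.** Minimisation needs categories. A test of whether age modifies the treatment effect does not, and section 9 has age collected at visit 0. Bands drawn for allocation discard some of the information on age. If the trial population resembles the Dutch cohort in section 1.5.5 ("average age 65 years old"), the youngest band will hold too few people to give a usable effect, and the test becomes in practice a comparison below and above 60.

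Centre raises a different problem. It is not a patient characteristic, and each centre will supply only a few dozen participants. A table of centre effects would be mostly noise, and some centres would probably appear to favour TENS even if FREMS worked equally well in all of them.

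At stake is the usefulness of the exploratory analysis: its chance of picking up an age trend, and the reading of a centre table.

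**Working it through.** **Inputs from the protocol.** Target difference 0.6, SD 1.65, 160 per group (320 evaluable), 356 recruited (section 14.1); 1:1 allocation and the age bands (6.4.2); mean age 65 (1.5.5); ten centres (Table 4 in 8.1: "Number of centres opened (NB: out of 10").

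**Assumed.** The protocol gives no age SD for this population, so 9 to 13 years is used, with 11 as the central value. Age is taken as normal, the age interaction as linear, and the centres as equal in size.

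**The plan's own figure.** n per group = 2 × (1.96 + 1.2816)² × 1.65² / 0.6² = 158.9 by the normal formula. The t-test needs 160, with power 90.0%. Then 320 / 0.9 = 355.6, so 356. The stated sample size is reproduced. No power is stated for any interaction.

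**Size of the age bands, mean 65.**
- Share aged 18-39 = Φ((40 − 65)/SD): 0.27% at SD 9 and 2.7% at SD 13, or about 1 to 10 of 356 over both arms.
- Share aged 60 or over = 1 − Φ((60 − 65)/SD): 71% at SD 9 and 65% at SD 13.
- Share of the age variance lying between bands: about 58 to 67% over SD 9 to 13, and about 62% at SD 11.

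**Power for a linear age interaction, N = 320, age SD 11.**
- SE of the interaction slope = 2 × 1.65 / (√320 × 11) = 0.0168 per year.
- Age in years: noncentrality = (slope / SE)², tested on 1 df. At 0.05 per year this is (0.05 / 0.01677)² = 8.89.
- Three bands: the noncentrality is multiplied by the between-band share and tested on 2 df. At the same slope this is 8.89 × 0.62 = 5.5.

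| Change in effect per decade (NRS points) | Age in years | Three bands, 2 df | Loss (points) |
|---|---|---|---|
| 0.1 | 9% | 7% | about 2 |
| 0.2 | 22% | 12% | 10 |
| 0.3 | 43% | 22% | 21 |
| 0.4 | 66% | 37% | about 30 |
| 0.5 | 84% | 54% | 30 |

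Simulation of 4,000 trials per slope gave 64% against 36% at 0.4 and 84% against 53% at 0.5. When the slope is instead chosen to give 80% power with age in years, the loss runs from 22 to 43 points over means of 60 to 68 and SDs of 8 to 14. A 1-df trend across the bands recovers part of it: about 65% at 0.5 per decade.

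**Centre.**
- 320 / 10 = 32 evaluable participants per centre, 16 per arm.
- SE = 1.65 × √(2/16) = 0.583. The 95% half-width is 1.96 × 0.583 = 1.14 (1.19 with the t quantile).
- If the true effect is 0.6 in every centre, P(one centre's estimate favours TENS) = Φ(−0.6/0.583) = 0.152.
- P(at least one of ten) = 1 − (1 − 0.152)¹⁰ = 0.81. With 8 centres it is 0.66 and with 12 it is 0.90.
- At SD 3.0, the 3-month value in the Birmingham clinic data (1.5.4), the half-width is 2.08 and the chance is 0.97.
- At SD 1.65, the expected gap between the highest and lowest of ten centre estimates is about 1.8 points by chance alone.

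**The case against.** The strongest reply is that section 14.5 limits the variables and does not say how age must be coded. Section 14.2 calls the text an outline with a statistical analysis plan to follow, so continuous age is not forbidden. That is fair as far as it goes. But effects within subgroups require levels, the only definition of age given for these variables is the banded one, and centre is included by the rule itself. The text as it stands leads to the banded test and the centre table.

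Three stronger readings are tempting, and the protocol does not support them.

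- A reader might take a loss of about 30 points as a property of the plan. It is not. It depends on an age SD that the protocol does not give, on a linear trend, and on a steep slope: at 0.5 per decade, a benefit of 0.6 at age 65 vanishes 12 years away (0.6 / 0.05). At gentler slopes the loss is small and both tests are weak. Nor do the bands waste most of the information, since they keep more than half of the age variance.
- A reader might say that the centre effects will mislead. The planned interaction test guards against over-reading one centre, and the results are labelled hypothesis-generating. The 81% is the chance of at least one reversed sign, not of a wrong conclusion. It also assumes ten equal centres, while section 8.1 allows more to be opened.
- A reader might extend the point to the adjusted models and ask for age in years there too. Nothing shown here supports that. Adjusting for the minimisation factors, as section 14.2 plans, is standard.

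**Conclusion.** The point holds as an improvement to an exploratory analysis. Followed as written, sections 14.5 and 6.4.2 give a youngest age band of roughly 1 to 10 people in 356, a less powerful age test than the collected data allow, and about ten centre effects, each with an interval of about ±1.1 points around a target of 0.6. Single-centre effects of that precision cannot be interpreted, and an apparent reversal somewhere is to be expected by chance.

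The direction of the age result needs only an approximately linear trend. Its size rests on the assumed age SD and slope and should be quoted as a range. The centre result rests on SD 1.65 and ten equal centres. The primary analysis, the sample size and the type I error of the main comparison are unaffected.

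**What to change.** In section 14.5:

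- Test intervention-by-age with age in years, as a linear term with a spline as a check, and report the estimated effect at a few chosen ages. Keep the three bands for allocation and descriptive display.
- Remove centre from the subgroup list. If variation between centres is of interest, report only the SD of a random intervention-by-centre effect.
- While the section is open, correct its cross-reference: it points to section 5 for the minimisation algorithm, which is in 6.4.2.

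This costs about two sentences in the protocol, carried into the statistical analysis plan, and needs no new data. The small downside is that a linear term assumes a smooth trend, which the spline checks.
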